#### 11.3.1 Primary Cohort:

APEC1621A will evaluate a primary cohort of 20 mutation-matched ("biomarker positive") evaluable patients of any histology for the primary study aim of determining the objective response rate (CR/PR according to the response criteria in [Section 12.3](#)) to LOXO-101 (larotrectinib). Using an A'Hern design with alpha=10%, a sample of N=20 will provide 90% power to detect an improvement in response rate from 5%, if the treatment is ineffective, to 25% if the targeted therapy is sufficiently effective to warrant further study. If there are at least 3 responses out of 20 in the primary cohort, the biomarker/therapy match will be deemed a success.

#### 11.3.2 Histology-Specific Biomarker Positive Expansion Cohorts:

If at any time  $\geq 3$  patients in the primary cohort with the same histology show signs of objective response (CR/PR according to the response criteria in [Section 12.3](#)),

a histology-specific biomarker positive expansion cohort will open after the primary cohort is completed to up to 7 evaluable patients for a total sample size of 10 evaluable biomarker positive patients with that histology. This will allow us to estimate more precisely the activity in biomarker positive patients of that histology. See [Appendix VIII](#) for a list of target tumor histologies.

We will open up to 3 such expansion cohorts for biomarker positive patients (i.e., if 3 histologies have  $\geq 3$  responses, we will open a total of 3 expansion cohorts as described above). Note that this can only happen if the response rate in the primary cohort is at least 45% (9/20) and there cannot be more than 21 additional evaluable patients in total for these expansion cohorts.

#### 11.4 **Methods of Analysis**

Response criteria are described in [Section 12](#). A responder is defined as a patient who achieves a best response of PR or CR on the study. Response rates will be calculated as the percent of evaluable patients who are responders, and confidence intervals will be constructed using the Wilson score interval method. Decision making for A'Hern design cohorts will follow rules described above.

Toxicity tables will be constructed to summarize the observed incidence by type of toxicity and grade. A patient will be counted only once for a given toxicity for the worst grade of that toxicity reported for that patient. Toxicity information recorded will include the type, severity, time of onset, time of resolution, and the probable association with the study regimen.

#### 11.5 **Evaluability for Response**

Any eligible patient who is enrolled and receives at least one dose of protocol therapy will be considered evaluable for response. Any patient who receives non-protocol anti-cancer therapy during the response evaluation period will be considered a non-responder for the purposes of the statistical rule, unless they show an objective response prior to receiving the non-protocol anti-cancer therapy (in which case they will be considered a responder). Patients who demonstrate a complete or partial response confirmed by central review will be considered to have experienced a response. When opening expansion cohorts, the evaluation period for determination of best response will be 6 treatment cycles. All other patients will be considered non-responders. Patients who are not evaluable for response evaluation may be replaced for the purposes of the statistical rule. All patients considered to have a response (CR or PR) must have imaging studies reviewed centrally at the COG. Centers will be notified by the COG about requests for scans of patients with stable disease. Preliminary assessment of activity using institutionally provided tumor measurements will be entered into CDUS quarterly. The central review by COG will be provided as the final reviewed assessment of response when such becomes available.

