## 2.0 BACKGROUND

### 2.1 Introduction/Rationale for Development

The TRK family are receptor tyrosine kinases involved in nervous system development. *NTRK1*, *NTRK2* and *NTRK3* encode TRKA, TRKB and TRKC respectively. TRK receptors are expressed in the nervous system and diseases resulting from loss of function mutations in NTRK genes reveal important roles for TRK in pain sensation, appetite control, memory and balance. Gene fusions involving each of the NTRK genes have been identified in a wide range of malignancies including the following seen in pediatric patients: gliomas, mesoblastic nephroma, and infantile fibrosarcoma.

The reported TRK fusions occurring in cancer have the 3' region of TRK including the kinase domain fused to the 5' sequence from another gene. For example, the *ETV6-NTRK3* fusion identified in mesoblastic nephroma, infantile fibrosarcoma and other malignancies has a varying breakpoints but always contains the kinase domain of TRKC and the SAM dimerization domain of ETV6. It has been thought that the *ETV6-NTRK3* fusion was pathognomonic for infantile fibrosarcoma. However, a recent case in which a novel *EML4-NTRK3* fusion was identified in a case with histology and clinical presentation consistent with a more aggressive manifestation of infantile fibrosarcoma raises the possibility that other TRK fusions may be identified in this disease. Infantile fibrosarcoma is rare, often treatable with surgery or chemotherapy and infrequently metastatic or recurrent. However, locally aggressive cases do occur and medical management is considered in these cases. Likewise, mesoblastic nephroma has an excellent prognosis with surgery alone. Thus, these pediatric diseases in which *NTRK* fusions are common are less likely to need therapy on a phase 2 trial such as the pediatric MATCH study. In diffuse intrinsic pontine glioma (DIPG) and other pediatric high grade gliomas *NTRK* fusions were identified in 8 of 112 cases sequenced. These pediatric malignancies, particularly DIPG have a poor prognosis.

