## 7.0 SUPPORTIVE CARE AND OTHER CONCOMITANT THERAPY

### 7.1 Concurrent Anticancer Therapy

Concurrent cancer therapy, including chemotherapy, radiation therapy, immunotherapy, or biologic therapy may NOT be administered to patients receiving study drug. If these treatments are administered the patient will be removed from protocol therapy.

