### 12.3.1 Definitions

#### 12.3.1.1 Evaluable for objective response:

Eligible patients who receive at least one dose of protocol therapy will be considered evaluable for response. Evaluable patients who demonstrate a complete or partial response confirmed by central review before receiving non-protocol anti-cancer therapy will be considered a responder. All other evaluable patients will be considered non-responders.

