12.8.4 Evaluation of organ enlargement

Complete Response (CR): Regress to normal

Partial response (PR): Spleen must have regressed by >50% in length beyond normal

Stable Disease (SD): No increase consistent with progression

Progressive Disease (PD): In the setting of splenomegaly, the splenic length must increase by 50% of the extent of its prior increase beyond baseline. If no prior splenomegaly, must increase by at least 2 cm from baseline.

New or recurrent splenomegaly

12.9 **Best Response**

Two objective status determinations of disease status, obtained on two consecutive determinations, separated by at least a 3 week time period, are required to determine the patient's overall best response. Two objective status determinations of CR before progression are required for best response of CR. Two determinations of PR or better before progression, but not qualifying for a CR, are required for a best response of PR. Two determinations of stable/no response or better before progression, but not qualifying as CR or PR, are required for a best response of stable/no response; if the first objective status is unknown, only one such determination is required. Patients with an objective status of progression on or before the second evaluations (the first evaluation is the first radiographic evaluation after treatment has been administered) will have a best response of progressive disease. Best response is unknown if the patient does not qualify for a best response of progressive disease and if all objective statuses after the first determination and before progression are unknown.

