12.9.1 Evaluation of Best Overall Response

The best overall response is the best response recorded from the start of the treatment until disease progression/recurrence (taking as reference for progressive disease the smallest measurements recorded since the treatment started). The

patient's best response assignment will depend on the achievement of both measurement and confirmation criteria.

Table 5. Sequences of overall response assessments with corresponding best response.

1 st Assessment	2 nd Assessment	Best Response
Progression		Progressive disease
Stable, PR, CR	Progression	Progressive disease
Stable	Stable	Stable
Stable	PR, CR	Stable
Stable	Not done	Not RECIST classifiable
PR	PR	PR
PR	CR	PR
PR, CR	Not done	Not RECIST classifiable
CR	CR	CR

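### Sections 11.5 and 12.3.1.1 classify differently a patient who responds and then receives other anti-cancer therapy before the response is confirmed

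*Combined protocol and SAP*

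**What the plan says.** Four places bear on who counts as a responder.

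- **Section 11.5.** Other anti-cancer therapy during the response evaluation period makes the patient a non-responder, "unless they show an objective response prior to receiving the non-protocol anti-cancer therapy (in which case they will be considered a responder"). The following sentence credits responses confirmed by central review but sets no timing relative to other therapy. A later sentence makes everyone else a non-responder.
- **Section 12.3.1.1.** "Evaluable patients who demonstrate a complete or partial response confirmed by central review before receiving non-protocol anti-cancer therapy will be considered a responder". All remaining evaluable patients are non-responders.
- **Sections 11.4 and 12.9.** Section 11.4 defines a responder by best response. Section 12.9 says: "Two determinations of PR or better before progression, but not qualifying for a CR, are required for a best response of PR". Two determinations are likewise needed for CR. Table 5 in Section 12.9.1 labels a PR or CR with no second assessment "Not RECIST classifiable".
- **Section 12.3.** A confirmatory scan is due in the cycle after the first documented response.

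No order of precedence is given. *Confirmed* means central review in 11.5 and 12.3.1.1, but a second assessment in 12.3 and 12.9. The other therapy that triggers these rules is not defined. Section 7.1 comes closest ("Concurrent cancer therapy, including chemotherapy, radiation therapy, immunotherapy, or biologic therapy may NOT be administered to patients receiving study drug"), but its list is open-ended and concerns staying on treatment, not classifying response.

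**The concern.** The primary endpoint is a count of responders compared with 3 of 20. The first disease evaluation falls at the end of cycle 2 and the confirmatory scan one cycle later, so every first response is followed by about 28 days in which it is unconfirmed. If a patient starts another treatment in that window, the plan gives two answers and no rule for choosing between them. The choice could then be made after the count is known. At stake are the reported response rate and its interval, the go decision if the count is near 3, and the opening of an expansion cohort, which Section 11.3.2 ties to at least 3 responders of the same histology.

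**Working it through.** **Classification.** Take a patient with PR at the end of cycle 2 who starts another anti-cancer agent before the cycle 3 scan.

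| Rule | Result |
|---|---|
| 11.5, exception clause | Responder: an objective response preceded the other therapy |
| 12.3.1.1, read literally | Non-responder: not confirmed before the other therapy |
| 11.4 with 12.9, second scan not done | Best response is not PR or CR, so not a responder |

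If the second scan is done after the other therapy has begun, 12.9 does not say whether it may serve as confirmation. The denominator is unaffected, because 11.5 and 12.3.1.1 both treat an eligible patient with at least one dose as evaluable.

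**The plan's design figures (Section 11.3.1).** Inputs: n = 20, success if X ≥ 3, null rate 5%, target rate 25%, stated alpha 10%, stated power 90%. X is binomial and P(X ≥ 3) = 1 − P(0) − P(1) − P(2).

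- At 5%: 1 − 0.35849 − 0.37735 − 0.18868 = 0.0755.
- At 25%: 1 − 0.00317 − 0.02114 − 0.06695 = 0.9087.

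The design reproduces: attained alpha is 7.55%, under the 10% ceiling, and power is 90.9%.

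**One patient.** Suppose two responders are undisputed and one patient is as described. The Wilson intervals below use the 90% level of the Section 11.3 table.

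- 11.5 exception: 3/20 = 15% (6.2% to 32.2%), success.
- 12.3.1.1: 2/20 = 10% (3.4% to 26.2%), not a success.

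**How often one patient could decide the result.** The 11.5 count must be exactly 3 and one of those three must be the patient in question. So P(X = 3) = 1140 p³(1 − p)¹⁷ is an upper bound:

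- p = 5%: 1140 × 0.000125 × 0.41812 = 0.0596.
- p = 25%: 1140 × 0.015625 × 0.0075169 = 0.1339.
- p = 50%: 1140 / 1,048,576 = 0.0011.

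**Several such patients (assumption).** Suppose the design rates count responses as the 11.5 exception does, and a share f of responders receives other therapy before confirmation. The documents give no value for f. The 12.3.1.1 count is then binomial with rate p(1 − f). It never exceeds the 11.5 count, so the chance that the two rules disagree on the decision is the difference in P(X ≥ 3).

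| f (assumed) | Power under 12.3.1.1 | Disagreement at 25% | Alpha under 12.3.1.1 | Disagreement at 5% |
|---|---|---|---|---|
| 0% | 0.9087 | 0 | 0.0755 | 0 |
| 5% | 0.8867 | 0.0220 | 0.0668 | 0.0087 |
| 10% | 0.8606 | 0.0481 | 0.0586 | 0.0169 |
| 20% | 0.7939 | 0.1148 | 0.0439 | 0.0316 |
| 40% | 0.5951 | 0.3136 | 0.0210 | 0.0545 |

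At 40% the disagreement at the 25% rate exceeds 13.4%, because with two or more such patients a count of 4 or higher can also drop below 3. The P(X = 3) bound applies to a single patient.

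Conversely, if 5% is a confirmed-response rate and the 11.5 exception adds 1 or 2 points (assumption), P(X ≥ 3) becomes 11.5% at 6% or 16.1% at 7%, against the stated 10%.

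**The case against.** The strongest reply is that Section 11 should be read as a whole. Sections 11.3.1 and 11.3.2 tie objective response to the criteria in 12.3, which contains 12.3.1.1. Section 11.4 relies on best response, and 12.9 requires two determinations. Section 11.5 itself goes on to require central review and to make all other patients non-responders. A single rule is available on that reading: a qualifying response before any other therapy. In 12.3.1.1, *before* may also attach to the response and not to the read, which narrows the gap for responses that central review later upholds. This part stands: the texts can be harmonised. But the exception in 11.5 still says in plain words that the patient is a responder, and nothing tells the analyst to override it.

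Several stronger readings are tempting and are not supported.

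- **A third endpoint status.** The Table 5 label is a best-response category. It is not CR or PR, so 12.3.1.1 makes the patient a non-responder.
- **Status set by the date of the central read.** This follows from only one grammatical reading of 12.3.1.1.
- **Resection credited to the drug as response.** A reader might infer this because 7.1 does not name surgery and 2.1 says: "Infantile fibrosarcoma is rare, often treatable with surgery or chemotherapy and infrequently metastatic or recurrent". But the list in 7.1 is open, and 2.1 goes on to say that these diseases are less likely to need a trial of this kind. Section 8.2.1 sends the baseline and all on-therapy evaluations of responders to central review. No document gives a rate, so no effect on type I error can be calculated.
- **A go decision generally at risk.** Section 2.4 reports confirmed partial responses in 6 of 7 assessable fusion-positive patients. If activity here is anywhere near that, the count will be well clear of 3.

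**Conclusion.** The inconsistency is real but limited. For a patient with one PR followed by other therapy before the confirmatory scan, the 11.5 exception and 12.3.1.1 give opposite results, and no precedence is stated. Each such patient moves the response rate by 5 points. For one such patient, the chance of reversing the go decision is at most 6.0% at a true rate of 5%, 13.4% at 25% and about 0.1% at 50%. It also requires that a counted responder actually be in this situation, for which the documents give no frequency. The more durable effects are on the reported rate and interval, and on the histology trigger: going from 2 to 3 responders in one histology opens a cohort of up to 7 further evaluable patients.

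The design itself reproduces and is not in question. This is a wording repair to make before responses are finally classified, and not a flaw that undermines the trial.

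**What to change.** Put one responder sentence in both 11.5 and 12.3.1.1, and delete the exception in 11.5. In line with 12.9: a responder is a patient whose first and confirming CR/PR scans were both acquired before any non-protocol anti-cancer therapy and are upheld on central review, whatever the date of the read. This also separates the two meanings of *confirmed*.

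Add, for response classification only, that disappearance or shrinkage of a lesion through resection or other local treatment does not count as CR or PR. List separately the patients with an unconfirmed response before other therapy, so that readers can see how many there were. Leave 7.1 unchanged, since it governs removal from treatment.

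The cost is wording in two sections. Sample size, decision rule and treatment stay as they are. A patient with an unconfirmed response before other therapy becomes a non-responder, so the response rate may be slightly lower. The sponsor could choose to credit such patients instead, but that would depart from the two-determination rule, and 11.4, 12.3.1.1 and 12.9 would then have to be changed to match.

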#### 11.6 **Evaluability for Toxicity**

All eligible patients who receive at least one dose of protocol therapy (will be considered in the evaluation of toxicity).

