## 4.0 PATIENT ELIGIBILITY

All clinical and laboratory studies to determine eligibility must be performed within 7 days prior to enrollment unless otherwise indicated. Laboratory values used to assess eligibility must be no older than seven (7) days at the start of therapy. Laboratory tests need **not** be repeated if therapy starts **within** seven (7) days of obtaining labs to assess eligibility. If a post-enrollment lab value is outside the limits of eligibility, or laboratory values are older than 7 days, then the following laboratory evaluations must be re-checked within 48 hours prior to initiating therapy: CBC with differential, bilirubin, ALT (SGPT) and serum creatinine. If the recheck is outside the limits of eligibility, the patient may not receive protocol therapy and will be considered off protocol therapy. Imaging studies, bone marrow biopsy and/or aspirate (when applicable) must be obtained within 14 days prior to start of protocol therapy (repeat the tumor imaging if necessary).

Clarification in timing when counting days: As an example, please note that if the patient's last day of prior therapy is September 1st, and the protocol requires waiting at least 7 days for that type of prior therapy, then that patient cannot be enrolled until September 8th.

**Important note:** The eligibility criteria listed below are interpreted literally and cannot be waived. All clinical and laboratory data required for determining eligibility of a patient enrolled on this trial must be available in the patient's medical or research record which will serve as the source document for verification at the time of audit.

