## 11.0 STATISTICAL AND ETHICAL CONSIDERATIONS

### 11.1 Sample Size and Study Duration

APEC1621A will require a minimum of 20 evaluable patients, and a maximum of 49 patients, allowing for 15% inevaluable. Assuming an enrollment rate of 4-9 biomarker positive patients per year, the primary cohort of this subprotocol is expected to be completed within 2.7-6 years.

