##### 14.4.2 Monitoring by the Study Chair and MATCH Leadership

The study chair will monitor the study regularly and enter evaluations of patients' eligibility, evaluability, and dose limiting toxicities into the study database. In addition, study data and the study chair's evaluations will be reviewed by the MATCH Chair, Vice Chair and Statistician on a weekly conference call.

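### Section 11.6 leaves a treated patient later ruled ineligible out of the toxicity tables, and no response analysis covers all treated patients

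*Combined protocol and SAP*

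**What the plan says.** Section 11.6 sets the toxicity population: "All eligible patients who receive at least one dose of protocol therapy (will be considered in the evaluation of toxicity" (the stray bracket is in the source). Section 11.5 uses the same two conditions for response: "Any eligible patient who is enrolled and receives at least one dose of protocol therapy will be considered evaluable for response". Section 12.3.1.1 repeats them. Section 11.5 then adds: "Patients who are not evaluable for response evaluation may be replaced for the purposes of the statistical rule".

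Section 11.1 plans for "a maximum of 49 patients, allowing for 15% inevaluable". It does not divide that 15% into patients never dosed and patients dosed but ineligible.

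On who decides, Section 14.4.2 has the study chair "enter evaluations of patients' eligibility, evaluability, and dose limiting toxicities into the study database". The next sentence says that study data and those evaluations "will be reviewed by the MATCH Chair, Vice Chair and Statistician on a weekly conference call". On how strictly the criteria are read, Section 4.0 states: "The eligibility criteria listed below are interpreted literally and cannot be waived". It also requires source records to be available for verification at audit.

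**The concern.** Aim 1.2.2 asks about tolerability in children who receive the drug. Exposure does not become less real because an eligibility failure is found later. Such failures can arise after dosing: Section 4.0 foresees audit against source, and Section 3.5 makes a patient ineligible if treatment began before enrollment.

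The failures also need not be neutral for safety. The limits on counts, creatinine, bilirubin and ALT in Section 4.1.6 are eligibility criteria. So is the bar on strong CYP3A4 inhibitors in Section 4.2.2.5, and Section 9.1.7 says these raise larotrectinib concentrations. A child found late to have breached one of these is informative about tolerability, yet would be absent from the tables.

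For response, removing and replacing a dosed patient changes who is counted in a rule designed for 20. If that happened more readily for non-responders, the rule of 3 responses would in effect draw on more than 20 patients. No section fixes when the eligibility ruling must be made or says that it is made without knowledge of outcome, and no all-treated response rate would let a reader check.

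**Working it through.** **Inputs.** From Sections 11.3 and 11.3.1: N = 20, success at 3 or more responses, null rate 5%, target rate 25%, alpha 10%, power 90%. From Section 11.1: 15% inevaluable and a maximum of 49. From Section 11.3.2: at most 21 further evaluable patients.

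**Step 1: reproduce the plan.** With X binomial(20, p), the chance of success is 1 − P(0) − P(1) − P(2).
- At p = 0.05: 1 − 0.3585 − 0.3774 − 0.1887 = 0.0755 (0.07548 before rounding, so 7.5%). This is within the stated 10%, which is a ceiling.
- At p = 0.25: 0.9087, which agrees with the stated 90%.
- Enrollment: 20/0.85 = 23.5, rounded up to 24. For the maximum, (20 + 21)/0.85 = 48.2, rounded up to 49, as stated. 24/9 = 2.7 and 24/4 = 6 years also match Section 11.1.

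The design figures are sound.

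**Step 2: who can be excluded.** Under Sections 11.5 and 12.3.1.1 an enrolled patient is inevaluable by never being dosed or by being dosed but ineligible. Only the second group matters here. For the primary cohort the allowance is 24 − 20 = 4, so I take k, the number dosed and ineligible, from 0 to 4. This range is an assumption, because the documents give no figure for k.

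**Step 3: upper bound for response.** Suppose k dosed non-responders are ruled ineligible and replaced, and every responder is kept. The 20 patients counted then show 3 or more responses whenever the 20 + k treated patients do, so the chance of success at a true 5% is P(X ≥ 3) with n = 20 + k.

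| k | n | Chance of success at a true 5% |
|---|---|---|
| 0 | 20 | 7.5% |
| 1 | 21 | 8.5% |
| 2 | 22 | 9.5% |
| 3 | 23 | 10.5% |
| 4 | 24 | 11.6% |

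For k = 4: 1 − 0.2920 − 0.3688 − 0.2232 = 0.1159. The stated 10% is passed from k = 3. If replacement is unrelated to response, the 20 counted patients behave as a random sample and the figure stays at 7.5%, whatever k is.

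**Step 4: toxicity tables.** Take 24 treated patients with 4 left out, again the upper end of the range, and exclusion unrelated to toxicity. An event that occurred in one patient is missing from the tables with probability 4/24 = 16.7%. One that occurred in two patients is missing altogether with probability (4 × 3)/(24 × 23) = 2.2%.

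**The case against.** The strongest reply is that little is really at risk.

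- **The data are kept.** A reader might infer that safety data from exposed children are lost. The documents do not support that. Section 10.2 requires adverse events to be followed and reported for 30 days after the last dose, Section 13.2 (Table A) requires serious events to be reported, and Section 14.2 sends routine and expedited events to CDUS, none of them limited to eligible patients. The loss is confined to the summary tables and their denominator.
- **The chair does not rule alone.** Section 14.4.2 provides weekly review by the MATCH leadership and the statistician. That the chair knows each patient's response is a reasonable inference in an open single-arm study, but it is not written; the section names dose-limiting toxicities, not response. The weekly review is a real safeguard, though it is not described as blind and no time for the ruling is set.
- **Literal criteria cut both ways.** A rule that cannot be waived removes ineligible responders too, which leaves little room for selection. Central review protects the response call, but not the choice of who is counted.
- **Late ineligibility should be uncommon.** Sections 3.4 and 3.5 require a signed checklist and completed screening before enrollment. Sections 4.0 and 8.1 require a recheck within 48 hours before treatment when laboratory values are out of date.
- **One planned analysis carries no such limit.** Section 11.7 defines progression-free survival from the start of treatment without an eligibility condition. The gap is in toxicity and response.

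These points reduce the likely size of the problem. They do not change the wording of Section 11.6 or supply an all-treated response rate.

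**Conclusion.** The point holds as a small, inexpensive correction. On its wording, Section 11.6 leaves dosed but ineligible patients out of the toxicity tables that serve Aim 1.2.2. Sections 11.5 and 12.3.1.1 do the same for response, with replacement allowed and no all-treated response rate to set beside the primary result.

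The response figures, up to 11.6% against a stated 10%, are a hypothetical upper bound. They require that several dosed patients are ruled ineligible, that all are non-responders, that all are replaced and that every responder stays. Nothing in the documents shows that this is intended or expected. A reader might also take 49 − 41 = 8 of 49 as the number of treated children who would vanish from both analyses. That figure is the whole inevaluable allowance, and Section 10.1(g) and (j) shows that some patients may enroll and never be treated. The number dosed and ineligible could be zero.

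Nor does the point justify changing the primary response set. Allowing replacement only when ineligibility is ruled before the first disease evaluation would keep patients with substantive failures in the primary denominator, such as no measurable disease or prior TRK-inhibitor treatment, if these were found later.

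**What to change.** In Section 11.6, delete the word eligible, so that toxicity is evaluated in every patient who receives at least one dose, whatever the later eligibility ruling. Keep the primary response set and the rule of 3 responses in 20 as planned. In Section 11.4 or 11.5, add the response rate in all treated patients as a sensitivity analysis, with the Wilson interval already specified. Add a listing of every dosed patient excluded from the primary set, giving the reason, the date of the ruling and the response.

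The adverse-event data are already collected. The cost is one extra table with its listing, and toxicity tables that will include a few patients outside the eligibility criteria.
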